8.6 Stopping Rules

Monitoring rules are described above in [Section 8.5](#).

For the purposes of stopping rules, Baseline is defined as the average of Day 1 pre-dose assessment and the last measurement prior to Day 1.

8.6.1 *Stopping Rules for Liver Chemistry Elevations*

In the event of confirmed laboratory results meeting any of the following criteria, dosing of a patient with Study Drug will be stopped permanently:

1. ALT or AST > 8 x ULN, which is confirmed
2. ALT or AST > 5 x ULN, which is confirmed and persists for \geq 2 weeks
3. ALT or AST > 3 x ULN (or the greater of 2 x Baseline value or 3 x ULN if the Baseline value was $>$ ULN), which is confirmed and total bilirubin $>$ 2 x ULN or INR $>$ 1.5
4. ALT or AST > 3 x ULN (or the greater of 2 x Baseline value or 3 x ULN if the Baseline value was $>$ ULN), which is confirmed, and the new appearance (i.e., onset coincides

with the changes in hepatic enzymes) of fatigue, nausea, vomiting, right upper quadrant pain or tenderness, fever, rash, or eosinophilia ($>$ ULN) felt by the Investigator to be potentially related to hepatic inflammation

8.6.2 Stopping Rules for Renal Function Test Results

In the event that any of the renal monitoring rules summarized in [Section 8.5.2](#) are met, treatment should immediately be interrupted and the abnormal result should be confirmed as soon as possible, but no later than 7 days after the initial event. In addition, upon consultation with the Study Medical Monitor, site will obtain any additional lab assessments necessary to determine any alternative etiologies that may account for the abnormal result. If results from additional testing confirm the initial abnormal lab result, future treatment of the patient will be determined per the guidelines below:

- An alternative etiology is identified that may account for abnormal results:
 - Patient will have treatment interrupted until either:
 - Lab values have returned to baseline, and/or
 - Alternative etiology has resolved/recovered, AND
 - Study Medical Monitor has approved treatment to resume
- An alternative etiology has not been identified that may account for abnormal results:
 - Patient will be permanently withdrawn from treatment

The follow-up schedule and frequency of renal function monitoring after the initial event will be determined by the Study Medical Monitor in consultation with the Investigator and the medical area specialist on the DSMB. The Investigator should consider consulting a local nephrologist for any change of renal function that presents a concern. If a renal biopsy is performed, a sample specimen should be made available for examination by an independent renal pathologist who has been engaged by the Sponsor to review such specimens.

8.6.3 Stopping Rule for Platelet Count Results

Actions to be taken in the event of a low platelet count are summarized in Table 3 below.

In the event of any platelet count less than $50,000/\text{mm}^3$, or a platelet count less than $75,000/\text{mm}^3$ that occurs while the patient is already on reduced dose, dosing of the patient with Study Drug will be stopped permanently (Table 3). Platelet count will be monitored daily until 2 successive values show improvement then monitored every 2-3 days until platelet count is stable.

Administration of glucocorticoids is recommended for patients whose platelet count is less than $25,000/\text{mm}^3$. Recovery in platelet count may be accelerated by administration of high dose glucocorticoids. Treatment guidelines for immune thrombocytopenia ([Provan et al. 2010](#)) recommend Dexamethasone 40 mg daily for 4 days every 2-4 weeks for 1-4 cycles; Prednis(ol)one 0.52 mg/kg/d for 2-4 weeks then taper; or methylprednisolone 30 mg/kg/day for 7 days (note: may require continuation with oral glucocorticoids after methylprednisolone).

In the event of a platelet count $< 75,000/\text{mm}^3$ and $\geq 50,000/\text{mm}^3$, and in the absence of major bleeding or clinically-relevant non-major bleeding (defined below; [Büller et al. 2007](#)), dosing of a patient with Study Drug should be suspended temporarily until the platelet count has recovered to $\geq 100,000/\text{mm}^3$. If dosing is continued, it must be at a reduced dose as shown in Table 3. The

suitability of the patient for continued dosing will be determined by the Investigator in consultation with the Study Medical Monitor and will be based on factors such as the original rate of decline in the patient's platelet count, whether any bleeding events were experienced by the patient, and the speed of recovery of platelet count after interruption of dosing.

If, after reintroduction of Study Drug, the platelet count again falls below 75,000/mm³, then dosing of the patient with Study Drug will be stopped permanently.

Once a patient commences weekly monitoring this frequency of monitoring should continue until the platelet count returns to the normal range ($\geq 140K/mm^3$) for 2 successive values.

Any unreportable platelet count result must be rechecked and determined not to have met a stopping rule before dosing can continue.

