8.5 Safety Monitoring Rules

Stopping rules are described below in [Section 8.6](#).

Please refer also to the “Guidance for Investigator” section of the Investigator’s Brochure.

For the purposes of safety monitoring Baseline is defined as the average of the pre-dose test closest to Day 1 and the Day 1 value itself.

In addition to the standard monitoring of clinical safety parameters, the following guidelines are provided for the monitoring of selected parameters chosen based on preclinical and clinical observations.

In case of discrepancy between the test results from 2 sources, such as between the central and local lab, safety-mandated action must be initiated based on the more critical (lower or higher, as relevant) of the 2 values.

Confirmation Guidance: At any time during the study (treatment or post-treatment follow-up periods), the clinical laboratory results meeting any of the safety monitoring criteria presented below must be confirmed by performing measurements (ideally in the same laboratory that performed the initial measurement) on new specimens prior to administering the next dose of Study Drug (ISIS 678354 or placebo). All new specimen collections should take place as soon as possible (ideally within 3 days of the initial collection).

In addition, as described in [Section 6.2.1](#) hematology labs should be sent in parallel to the central and local laboratory for analysis.

Stopping Rule Guidance: The Investigator may interrupt or permanently discontinue study treatment for any medical reason including changes in clinical laboratory results.

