8.5.3 Safety Monitoring for Platelet Count Results

All patients will have platelet counts monitored every 14 days (± 2 days) for the duration of the study treatment period and must not receive Study Drug without an interpretable platelet count result in the prior 14 days. Upon completion of the study treatment period, platelets will be monitored every 14 days (± 2 days) for the first 6 weeks and then at 8 and 13 weeks post end of treatment period (as per visit schedule).

As described in [Section 6.2.1](#), all platelet count results must be reviewed promptly (within 48 hours of receipt) by the Investigator or the designee to ensure that the count has not met the stopping rule and to determine whether the rate of decline is suggestive that the patient could be approaching the dose interruption rule of 75,000/mm³ as specified in [Section 8.6.3](#).

Any case of a platelet count reduction to levels below 50,000/mm³ (Grade 3 or Grade 4) is considered an adverse event of special interest and should be reported in an expedited fashion to the Sponsor. In this case the Investigator should refer the subject to a hematologist to provide diagnostic and therapeutic management.

Lab alerts related to platelet monitoring/stopping rules are issued when: 1) platelet counts are < 140,000 mm³, 2) platelet count is $\geq 30\%$ decreased from Baseline, or 3) the hematology sample is unreportable. All these lab alerts, are reviewed promptly by the Medical Monitor and instructions are communicated to the Investigator and the study personnel within 24 hours of receiving an actionable lab alert as described in [Section 6.2.1](#).

Actions to be taken in the event of reduced platelet count are shown in [Table 3](#) in [Section 8.6.3](#).

In the event of a platelet count < 100,000/mm³ the laboratory tests outlined in [Appendix E](#), should be performed as soon as possible. Additional lab tests will be determined by the Sponsor Medical Monitor or designee in consultation with the Investigator.

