8.6.4 Stopping Rule for Bleeding

If an event of Major Bleeding or Clinically-Relevant Non-major Bleeding event occurs, the Investigator must notify the Sponsor Medical Monitor (or designee) and the subject should be closely monitored (vital signs, lab tests such as Hb, HCT and platelet count, additional outpatient visits, overnight stays and coagulation tests may be needed) throughout the treatment and during the post-treatment evaluation period.

In the event of Major Bleeding or Clinically-Relevant Non-major Bleeding (see definitions in [Section 8.5.4](#)) as assessed by the Investigator, dosing of a subject with Study Drug (ISIS 678354 or placebo) may be stopped permanently. The follow-up schedule for any events meeting this stopping criterion will be determined, including the suitability of the subject for resumption of dosing by the Investigator in consultation with the Sponsor Medical Monitor (or designee).

Table 3 Actions in Patients with Low Platelet Count

Platelet Count on Rx	Drug Dose	Monitoring
Normal range, $\geq 140K/mm^3$	No action	Monitor every 14 days (± 2 days)
$\geq 100K$ to $< 140K/mm^3$	No action	Closer observation Monitor every week*
$\geq 75K$ to $< 100K/mm^3$	Permanently reduce as follows: For Cohort A: reduce to 5 mg every 4 weeks For Cohort B: reduce to 25 mg every 4 weeks For Cohort C: reduce to 7.5 mg every 2 weeks For Cohort D: reduce to 5 mg every week	Closer observation Monitor every week*
$\geq 50K$ to $< 75K/mm^3$	Pause dosing When platelet count returns to $\geq 100K/mm^3$ restart dosing as follows only if approved by Sponsor Medical Monitor: For Cohort A: reduce to 5 mg every 4 weeks For Cohort B: reduce to 25 mg every 4 weeks For Cohort C: reduce to 7.5 mg every 2 weeks For Cohort D: reduce to 5 mg every week or Permanently discontinue Study Drug if it occurs while on already reduced dose	Closer observation Monitor every 2-3 days until 2 successive values show improvement Consider discontinuation of antiplatelet agents/non-steroidal anti-inflammatory drug (NSAIDS)

Platelet Count on Rx	Drug Dose	Monitoring
≥25K to <50K/mm ³	Permanently discontinue Study Drug	Closer observation: Monitor daily until 2 successive values show improvement then monitor every 2-3 days until platelet count stable Discontinue antiplatelet agents/NSAIDS while platelet count <50K/mm ³ if possible Refer to hematologist to provide diagnostic and therapeutic management

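### For a reduced-dose patient whose platelets fall to 50,000 to below 75,000/mm³, Section 8.6.3 orders daily counts but Table 3 orders counts only every 2-3 days

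*Combined protocol and SAP*

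**What the plan says.** Protocol Section 8.6.3 introduces Table 3 as a summary of what to do when the platelet count is low. It then sets two triggers for a permanent stop in one sentence. The first is any count below 50,000/mm³. The second is a count below 75,000/mm³ "that occurs while the patient is already on reduced dose, dosing of the patient with Study Drug will be stopped permanently". The next sentence sets the monitoring and names neither trigger: "Platelet count will be monitored daily until 2 successive values show improvement then monitored every 2-3 days until platelet count is stable".

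Table 3 is printed under Section 8.6.4 and is organised by platelet band. In the band from 50,000 to below 75,000/mm³, the dose column pauses dosing for a patient on full dose, but for the other patient it says "Permanently discontinue Study Drug if it occurs while on already reduced dose". The monitoring column of that row has one entry for both cases: "Monitor every 2-3 days until 2 successive values show improvement". The rows for 25,000 to below 50,000/mm³ and for below 25,000/mm³ both carry the schedule of the body text: "Monitor daily until 2 successive values show improvement then monitor every 2-3 days until platelet count stable".

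Section 8.8 repeats the two triggers without a frequency. Section 8.8.1 sends patients who discontinue early back to the platelet rules of Table 3 and Section 8.6.3. Sections 8.5.3 and 8.12 set the routine 14-day schedule. None of them says which frequency applies here.

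**The concern.** A patient on a reduced dose whose count is, say, 60,000/mm³ meets the second trigger and is permanently discontinued under both the text and the table. The text then requires a count every day. The table requires one every 2-3 days. The end points differ too: the text continues until the count is stable, while the table row's schedule ends at 2 successive improvements.

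The table's single monitoring cell serves two different patients, one paused on full dose and one permanently stopped on a reduced dose. A site working from the table would follow the second patient less closely than Section 8.6.3 requires, just when the count has dropped below 75,000/mm³ despite a dose reduction.

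Platelet reduction is a named safety endpoint (Section 10.1.3) and a dose-selection consideration (Section 10.1.4). The SAP categorises each patient's nadir count (Section 3.7.4), and sparser sampling makes the true nadir easier to miss. Section 8.12 also requires documented compliance with the monitoring program and provides for discontinuing sites that cannot or will not comply, so sites need one unambiguous schedule.

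**Working it through.** The plan gives no figure of its own to reproduce. The check compares the rules that order a permanent stop and then counts scheduled samples.

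**Step 1. Rules side by side**

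| Source | Patient | Drug | Counts |
|---|---|---|---|
| Section 8.6.3 text | below 50,000/mm³, or below 75,000/mm³ on reduced dose | permanent stop | daily to 2 successive improvements, then every 2-3 days to stable |
| Table 3, 50,000 to below 75,000/mm³ | already on reduced dose | permanent stop | every 2-3 days to 2 successive improvements |
| Table 3, 25,000 to below 50,000/mm³ | any | permanent stop | daily, then every 2-3 days to stable |
| Table 3, below 25,000/mm³ | any | permanent stop | daily, then every 2-3 days to stable |

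Of the 3 table rows that order a permanent stop, 2 match the text and 1 does not.

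**Step 2. Scheduled counts.** Take the index count as day 0 and assume no 2 successive improvements through day 6. The 6-day window is chosen for illustration.

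- Section 8.6.3, daily: days 1, 2, 3, 4, 5, 6 = 6 counts.
- Table 3, every 2 days: days 2, 4, 6 = 3 counts. Shortfall 6 − 3 = 3.
- Table 3, every 3 days: days 3, 6 = 2 counts. Shortfall 6 − 2 = 4.

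**Step 3. Allow for the confirmatory retest.** Section 8.5 asks for a new specimen, ideally within 3 days of the initial collection. If it falls on a day not already in the series, it adds one count.

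- Every 2 days: 3 + 1 = 4. Shortfall 6 − 4 = 2.
- Every 3 days: 2 + 1 = 3. Shortfall 6 − 3 = 3.

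Across both cases the shortfall is 2 to 4 of 6 counts.

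**Step 4. Sensitivity to the assumption.** Suppose instead that every count improves from the start, and ignore any retest.

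- Section 8.6.3: days 1 and 2, then days 4 and 6 (every 2 days) or day 5 (every 3 days) = 4 or 3 counts.
- Table 3 row: days 2 and 4, or days 3 and 6 = 2 counts, after which the row sets no further schedule.

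The shortfall is then 1 to 2 counts. The gap matters most when recovery is slow.

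**The case against.** The strongest counter-argument is that Table 3 sets monitoring by platelet band, not by drug status. Daily counts begin below 50,000/mm³, and both rows there repeat the Section 8.6.3 sentence almost exactly. On that reading the daily sentence describes only the patient below 50,000/mm³, and there is no conflict. Sections 8.5.3 and 8.8.1 also direct sites to Table 3, and nothing in the documents shows that a patient at 60,000/mm³ who is permanently stopped needs more counts than one at the same level who is paused.

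The reading is possible, but it needs a limit that the text does not state. The daily sentence follows directly on a sentence naming both triggers. The paragraph after it, on glucocorticoids, states its own threshold (below 25,000/mm³) when a narrower group is meant. The references to Table 3 also cite Section 8.6.3 and do not say which frequency prevails. Even if the narrower meaning was intended, the wording would need correcting.

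The objection on weight largely stands:

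- Dosing has ended under both rules.
- The table still asks for closer observation, and a further fall below 50,000/mm³ moves the patient to daily counts and hematology referral.
- Under Section 8.5.3, "instructions are communicated to the Investigator and the study personnel within 24 hours of receiving an actionable lab alert".
- Weekly monitoring also applies as counts recover: "Once a patient commences weekly monitoring this frequency of monitoring should continue until the platelet count returns to the normal range".

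These safeguards soften the discrepancy, but none sets the frequency for the first days. It is also true that the shortfall counts blood draws, not missed events or harm.

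**Conclusion.** The concern holds. It is an internal inconsistency between two current safety rules for one defined patient: already on a reduced dose, count from 50,000 to below 75,000/mm³, drug permanently stopped. The shortfall is 2 to 4 of 6 scheduled counts over the first 6 days. That range assumes no 2 successive improvements in the window and at most one retest off the table's series.

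Severity is minor. A cautious site can satisfy both rules by counting daily, and no efficacy analysis is affected. The documents give no rate for a second fall on a reduced dose. Few such patients are likely, since Section 2.3.4 reports no treatment-related platelet abnormality in Phase 1. Confidence that the texts disagree is high. Which of the two the authors intended cannot be settled from the documents.

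**What to change.** Split the monitoring cell in the Table 3 row for 50,000 to below 75,000/mm³:

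- Dosing paused, patient on full dose: "Monitor every 2-3 days until 2 successive values show improvement" (unchanged).
- Permanently discontinued, patient already on a reduced dose: "Monitor daily until 2 successive values show improvement then monitor every 2-3 days until platelet count stable".

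This brings the summary table into line with the body text, uses wording already in the next two rows, and is the more protective direction. No dosing rule or analysis changes. The cost is one added line, plus about 2 to 4 extra blood draws over 6 days and some further draws until the count is stable, in rare patients.

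If the sponsor in fact meant daily counts only below 50,000/mm³, the alternative is to state that limit in the daily sentence of Section 8.6.3. That would also remove the conflict, but it would leave the reduced-dose patient on the sparser schedule.

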8.6.4 Stopping Rule for Bleeding

If an event of Major Bleeding or Clinically-Relevant Non-major Bleeding event occurs, the Investigator must notify the Sponsor Medical Monitor (or designee) and the subject should be closely monitored (vital signs, lab tests such as Hb, HCT and platelet count, additional outpatient visits, overnight stays and coagulation tests may be needed) throughout the treatment and during the post-treatment evaluation period.

In the event of Major Bleeding or Clinically-Relevant Non-major Bleeding (see definitions in [Section 8.5.4](#)) as assessed by the Investigator, dosing of a subject with Study Drug (ISIS 678354 or placebo) may be stopped permanently. The follow-up schedule for any events meeting this stopping criterion will be determined, including the suitability of the subject for resumption of dosing by the Investigator in consultation with the Sponsor Medical Monitor (or designee).

Table 3 Actions in Patients with Low Platelet Count

Platelet Count on Rx	Drug Dose	Monitoring
Normal range, $\geq 140K/mm^3$	No action	Monitor every 14 days (± 2 days)
$\geq 100K$ to $< 140K/mm^3$	No action	Closer observation Monitor every week*
$\geq 75K$ to $< 100K/mm^3$	Permanently reduce as follows: For Cohort A: reduce to 5 mg every 4 weeks For Cohort B: reduce to 25 mg every 4 weeks For Cohort C: reduce to 7.5 mg every 2 weeks For Cohort D: reduce to 5 mg every week	Closer observation Monitor every week*
$\geq 50K$ to $< 75K/mm^3$	Pause dosing When platelet count returns to $\geq 100K/mm^3$ restart dosing as follows only if approved by Sponsor Medical Monitor: For Cohort A: reduce to 5 mg every 4 weeks For Cohort B: reduce to 25 mg every 4 weeks For Cohort C: reduce to 7.5 mg every 2 weeks For Cohort D: reduce to 5 mg every week or Permanently discontinue Study Drug if it occurs while on already reduced dose	Closer observation Monitor every 2-3 days until 2 successive values show improvement Consider discontinuation of antiplatelet agents/non-steroidal anti-inflammatory drug (NSAIDS)

Platelet Count on Rx	Drug Dose	Monitoring
≥25K to <50K/mm ³	Permanently discontinue Study Drug	Closer observation: Monitor daily until 2 successive values show improvement then monitor every 2-3 days until platelet count stable Discontinue antiplatelet agents/NSAIDS while platelet count <50K/mm ³ if possible Refer to hematologist to provide diagnostic and therapeutic management
<25K/mm ³	Permanently discontinue Study Drug	Closer observation: Monitor daily until 2 successive values show improvement then monitor every 2-3 days until platelet count stable Steroids recommended** Consider need for hospitalization Discontinue antiplatelet agents/NSAIDS medication while platelet count <50K/mm ³ if possible Refer to hematologist to provide diagnostic and therapeutic management

* Once a patient commences weekly monitoring this frequency of monitoring should continue until the platelet count returns to the normal range (≥140K/mm³) for 2 successive values.

** Recovery in platelet count may be accelerated by administration of high dose glucocorticoids. Treatment guidelines for immune thrombocytopenia (Provan et al. 2010) recommend Dexamethasone 40 mg daily for 4 days every 24 weeks for 1-4 cycles; Prednis(ol)-one 0.5-2 mg/kg/d for 2-4 weeks then taper; or Methylprednisolone 30 mg/kg/day for 7 days (note: may require continuation with oral steroids after methylprednisolone).

8.7 Adjustment of Dose

Dose frequency adjustments for platelet count reduction must be made in accordance with Table 3 (above).

Other dose adjustments, including dose interruptions, and/or decreasing the dose will be allowed for safety or tolerability after consultation with the Sponsor Medical Monitor.

Patients may have their dose interrupted in response to AEs after consultation with Study Medical Monitor.

8.8 Discontinuation of Study Drug

A patient must permanently discontinue study treatment for any of the following:

- The patient becomes pregnant. Report the pregnancy according to instructions in [Section 9.5.4](#)
- The patient withdraws consent
- The patient experiences an AE that necessitates permanent discontinuation of Study Drug
- The patient develops laboratory test abnormalities that meet any of the stopping rules listed in [Sections 8.6.1](#) to [8.6.4](#)
- When a platelet count of less than 50,000/mm³, or a platelet count less than 75,000/mm³ while the patient is on a reduced dose.

The reason for discontinuation of Study Drug must be recorded in the electronic Case Report Form (eCRF) and source documentation.

8.8.1 *Follow-up Visits for Early Termination from Treatment Period or from Post-Treatment Follow-up Period*

Any patient who discontinues early from the treatment period or from the post-treatment follow-up period should be strongly encouraged to complete follow-up study visits, procedures and observations as described below.

Any patient who discontinues early from the treatment period or from post-treatment follow-up period should be followed as per the platelet monitoring rules shown in [Table 3, Section 8.6.3](#) for the first 6 weeks post end of treatment period and then at 8 and 13 weeks post end of treatment period (as per visit schedule).

If a patient early terminates from the treatment period, an ET visit (Week 53 visit assessments) should be performed at the time of withdrawal, and ideally within 2 weeks from the last dose of Study Drug, and patients should start the 13-week post-treatment follow-up period to collect the study assessments in accordance with the Schedule of Procedures in [Appendix A](#).

If the patient early terminates from the post-treatment follow-up period, a final visit (assessments from the Week 13 of post-treatment follow-up period) should be performed at the time of withdrawal.

